## Efficacy

- Overall response rate at 1-year as determined by the NIH Consensus Development Project Criteria, without secondary systemic immunosuppression and no recurrent malignancy or death
- Failure Free Survival (FFS) at 24 weeks and 1-year as defined as the time from the initiation of study therapy until treatment failure defined as the initiation of secondary therapy for chronic GVHD, malignancy relapse, or death from any cause.
- The proportion of patients who have withdrawn all immunosuppressants at 1-year.
- Overall response rate at 24 weeks, as determined by the NIH Consensus Development Project Criteria, stratified by concurrent prednisone (or equivalence) use: 0 mg/kg/d,  $\leq 0.25$ mg/kg/d, and  $> 0.25$ mg/kg/d.
- The mean cumulative prednisone dose used at 24 weeks.
- Organ-specific response rates at 24 weeks and 1-year as determined by the NIH Consensus Development Project Criteria.
- Change in NIH global score of chronic GVHD from baseline to 24 weeks and 1-year after the initiation of the protocol therapy. The NIH global score will be defined by using the NIH consensus criteria for the assessment of chronic GVHD severity.
- Duration of response (DOR), defined as the interval between the date of initial documentation of a response (PR or better), and the time of progression from the best response, the start of a new therapy for cGVHD (including corticosteroids), or death from any cause.
- Provider-reported chronic GVHD severity at baseline, 24 weeks, and 1-year.
- Patient-reported chronic GVHD severity at baseline, 24 weeks, and 1-year.
- 24 week and 1-year non-relapse mortality (NRM) defined as the proportion of participants who died due to causes other than a relapse of their primary hematologic disease.
- Relapse rate (RR) of malignant and non-malignant hematologic diseases, defined as the proportion of participants whose underlying disease relapses at 24 weeks and 1-year.
- Overall survival (OS) as defined as the time from the initiation of study therapy until death from any cause at 24 weeks and 1 year.

Observed proportions and exact binomial confidence intervals will be reported for binary endpoints with no censored events. These may include withdrawal from immunosuppressants at 1-year, the overall response at 24 weeks stratified by current prednisone use (0 mg/kg/d,  $\leq 0.25$ mg/kg/d, and  $> 0.25$ mg/kg/d.), the overall response at 1 year, organ-specific response at 24 weeks and 1 year, no recurrent malignancy, no

addition of new systemic treatment for chronic GVHD, and use of prednisone dose (or its equivalent) of  $\leq 0.5$  mg/kg/d at 24 weeks. Kaplan-Meier methods will be used for these binary endpoints if there are censored events. Kaplan –Meier methods and associated confidence intervals will be used for survival endpoints (FFS and OS). NRM and RR will be treated as competing risks and analyzed by computing nonparametric subdistribution functions. The minimum, maximum, mean, and median value along with interquartile range will be reported for continuous and ordered categorical endpoints (NIH global score of chronic GVHD, provider, and patient-reported GVHD severity). Change in continuous or ordered categorical endpoints (NIH global score of chronic GVHD, provider, and patient-reported GVHD severity) will be analyzed using paired Wilcoxon tests. The minimum, maximum, mean, and median cumulative prednisone dose at 24 weeks will be reported, along with the interquartile range.

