## 1 OBJECTIVES

### 1.1 Primary Objective

**1.1.1 Part 1:** To assess an appropriate dose of itacitinib in combination with Extracorporeal Photopheresis (ECP) in patients with moderate or severe chronic GVHD.

Primary Endpoint: The rate of dose-limiting toxicities during the defined DLT evaluation period.

**1.1.2 Part 2:** To assess the clinical efficacy of itacitinib in combination with ECP in subjects with moderate or severe chronic GVHD treated at the Recommended Phase 2 Dose (RP2D).

Primary Endpoint: Overall response rate (ORR) at 24 weeks (at Cycle 7 Day 1 visit) as determined by the NIH Consensus Development Project Criteria (ORR is defined as CR + PR) without secondary systemic immunosuppressive therapy and no recurrent malignancy or death.

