### 1.2 Secondary Objectives

**1.2.1** To assess the safety of itacitinib in combination with ECP.

Secondary Endpoint: Frequency of adverse events (AEs) and serious adverse events (SAEs) will be collected assessed by CTCAE, version 5.0 for the duration of treatment.

**1.2.2** To assess long term response and efficacy.

Secondary Endpoints:

- Overall response rate at 1-year as determined by the NIH Consensus Development Project Criteria, without secondary systemic immunosuppression and no recurrent malignancy or death
- Failure Free Survival (FFS) at 24 weeks and 1-year as defined as the time from the initiation of study therapy until treatment failure defined as the initiation of secondary therapy for chronic GVHD, malignancy relapse, or death from any cause.
- The proportion of patients who have withdrawn all immunosuppressants at 1-year.
- Overall response rate at 24 weeks, as determined by the NIH Consensus Development Project Criteria, stratified by concurrent prednisone (or equivalence) use: 0 mg/kg/d,  $\leq 0.25$ mg/kg/d, and  $> 0.25$ mg/kg/d.
- The mean cumulative prednisone dose used up to 24 weeks.

- Organ-specific response rates at 24 weeks and 1-year as determined by the NIH Consensus Development Project Criteria.
- Change in NIH global score of chronic GVHD from baseline to 24 weeks and 1-year after the initiation of the protocol therapy. The NIH global score will be defined by using the NIH consensus criteria for the assessment of chronic GVHD severity.
- Duration of response (DOR), defined as the interval between the date of initial documentation of a response (PR or better), and the time of progression from the best response, the start of a new therapy for cGVHD (including corticosteroids), or death from any cause.
- Clinician-reported chronic GVHD activity assessment at baseline, 24 weeks, and 1-year.
- Patient-reported chronic GVHD severity assessment at baseline, 24 weeks, and 1-year.
- 24 week and 1-year non-relapse mortality (NRM) defined as the proportion of participants who died due to causes other than a relapse of their primary hematologic disease.
- Relapse rate (RR) of malignant and non-malignant hematologic diseases, defined as the proportion of participants whose underlying disease relapses at 24 weeks and 1-year.
- Overall survival (OS) as defined as the time from the initiation of study therapy until death from any cause at 24 weeks and 1-year.

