## 4 STUDY DESIGN

### 4.1 Description

This is an open-label, Phase II trial designed to assess the recommended phase 2 dose (RP2D) of itacitinib in combination ECP and efficacy of the combination after 24 weeks of therapy. The trial will consist of two parts: Part One will assess the RP2D. For dose-finding purposes, the DLT evaluation period will be defined as the time from the first dose of itacitinib lead-in (7-day lead-in) to the last day of cycle one combination therapy (cycle one day 28). Part Two will further describe and characterize the safety and efficacy of the regimen. The RP2D will be determined by a 3+3 dose de-escalation design. Should dose level one be deemed intolerable, enrollment will proceed at dose level -1. The RP2D will be affirmed according to the rules of the 3+3 dose de-escalation scheme (Section 4.2). Once an RP2D has been confirmed, Part 2 will open as an expansion cohort. Safety will be monitored during the trial as described in Section 11.3.

All eligible patients will begin study therapy with approximately a week lead-in of itacitinib monotherapy. After completing the itacitinib lead-in, combination treatment will begin in 28-day cycles. After eight weeks of combination therapy, patients will begin an ECP taper and continue on itacitinib for a total of 6 cycles. Patients achieving PR or better may

continue on itacitinib for up to 1 year. Patients will remain on study therapy as long as treatment discontinuation criteria are not met.

Prednisone dose (or prednisone equivalent) at  $\leq 0.25$  mg/kg/d for treatment of GVHD progressing or not sufficiently responding to study treatment will be allowed, at the discretion of the treating investigator and with approval of the PI, while the participant is on study treatment. Addition of prednisone dose (or prednisone equivalent) at  $\leq 0.25$  mg/kg/d will not be considered as failure of the primary endpoint. Prednisone doses (or prednisone equivalent) of  $> 0.25$  mg/kg/d but  $\leq 0.5$  mg/kg/d for more than 8 weeks or  $> 0.5$  mg/kg/d once will count as a failure of the primary endpoint, but the participant will be allowed to remain on the treatment period of the study. If the participant requires any systemic immunosuppression besides prednisone (i.e., ibrutinib, ruxolitinib, etc.), the participant will be withdrawn from study treatment but remain on study for follow-up.

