## **12.4 Statistical Analysis**

### **12.4.1 Primary Endpoint Analysis**

#### **Part 1**

The primary objective is to assess the safety and tolerability of itacitinib and ECP in subjects with chronic GVHD and to determine the RP2D. Adverse events (AEs), serious adverse events (SAEs), and dose-limiting toxicities (DLTs) are primary endpoints.

All subjects who receive any study treatment will be included in the final summaries and listings of safety data. Detailed information collected for each AE will include a description of the event, duration, severity, relatedness to study drugs, action taken, and clinical outcome. The severity of the AEs will be graded according to the CTCAE v5.0. The statistical analysis of the safety data will be descriptive and tabular in nature.

## Part 2

Simon's optimal two-stage design will be used in Part 2. The primary outcome is the overall response rate (CR + PR) at 24 weeks. Withdrawal or progression prior to 24 weeks or missing 24-week assessment will be considered non-response. After the first 16 patients treated at the RP2D complete 24 weeks of therapy or meet treatment discontinuation criteria, enrollment will be put on hold and an interim analysis will be conducted. This study treatment will be considered promising if the overall response rate at 24 weeks is  $\geq 60\%$  and unacceptable if the overall response rate at 24 weeks is  $\leq 40\%$ . 50% is the reported best overall response rate of current first-line therapy with high-dose steroids. The null hypothesis that the true response rate is  $\leq 40\%$  will be tested against a one-sided alternative.

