### **12.4.3 Exploratory Endpoint Analysis**

#### **Duration of Response (DOR)**

Duration of response (DOR) is defined as the interval between the date of initial documentation of a response (PR or better), and the time of progression from the best response, the start of a new therapy for cGVHD (including corticosteroids), or death from any cause. DOR will be summarized for all responders. Non-responders will be excluded from the analysis of DOR. The median duration of response will be estimated using Kaplan-Meier methodology.

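### Organ-specific response omits the failure conditions that the ORR carries at the same time points, and duration of response omits relapse of the underlying disease

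*Combined protocol and SAP*

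**What the plan says.** The 24-week ORR in section 1.1.2 is CR plus PR by NIH criteria "without secondary systemic immunosuppressive therapy and no recurrent malignancy or death". The 1-year ORR in sections 1.2.2 and 12.4.2 carries the same three conditions, in the words "without secondary systemic immunosuppression and no recurrent malignancy or death".

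Organ-specific response appears in the same two lists as "Organ-specific response rates at 24 weeks and 1-year as determined by the NIH Consensus Development Project Criteria", and the definition stops there. Section 12.4.2 then gives the method: observed proportions with exact binomial intervals, or Kaplan-Meier if there is censoring.

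DOR (1.2.2, 12.4.2, 12.4.3) runs from first documented PR or better to progression from best response, "the start of a new therapy for cGVHD (including corticosteroids), or death from any cause". Section 12.4.3 adds that "DOR will be summarized for all responders".

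On patients who need systemic immunosuppression other than prednisone, section 4.1 says "the participant will be withdrawn from study treatment but remain on study for follow-up"; section 6.7.1 repeats this.

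**The concern.** Two endpoints read at the same visit can contradict each other for one patient: a non-responder overall but a responder in skin, mouth or another organ. If that organ improved on a second-line drug or on prednisone above the failure threshold, the organ table attributes to itacitinib plus ECP something that the ORR deliberately does not. In the same way, a patient whose malignancy relapses has failed for FFS, while DOR may go on counting time in response.

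This is a single-arm trial whose results are set against historical response to steroids (Study Summary, reference therapy). No control arm would share the inflation and offset it. Without a written rule, the analyst must also choose one after seeing the data.

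**Working it through.** **1. The plan's own figures.** The only stated operating characteristics concern the primary ORR: continue if more than 7 of 16 respond, and reject the null with 24 or more of 46. The exact probability of rejection is the sum over x = 8 to 16 of P(X1 = x) × P(Y ≥ 24 − x), with X1 ~ Bin(16, p) and Y ~ Bin(30, p).
- p = 0.40: 0.04859 (stated 0.0486).
- p = 0.60: 0.8006 (stated 80%).

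Both reproduce. They rest on the ORR, which has its conditions, so nothing below changes them.

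**2. The definitions side by side.**

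| Endpoint | Secondary systemic therapy | Recurrent malignancy | Death |
|---|---|---|---|
| ORR, 24 weeks (1.1.2) | failure | failure | failure |
| ORR, 1 year (1.2.2, 12.4.2) | failure | failure | failure |
| FFS (1.2.2, 12.4.2) | failure | failure | failure |
| Organ-specific response (1.2.2, 12.4.2) | not stated | not stated | not stated |
| DOR (1.2.2, 12.4.2, 12.4.3) | ends DOR | not stated | ends DOR |

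**3. Is the condition supplied elsewhere?** No.
- The rule "Withdrawal or progression prior to 24 weeks or missing 24-week assessment will be considered non-response" (12.1 and 12.4.1, Part 2) is attached to the primary outcome.
- The response-evaluable set (12.2.3) asks only for two weeks of combined treatment.
- The methods text in 12.4.2 has no rule for secondary therapy or relapse.

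**4. Can the data arise?** Yes, by two routes.
- *Switchers.* They stay on study. Section 9.5 follows them every 12 weeks for 12 months, and Table 7 schedules a chronic GVHD assessment in follow-up. A patient leaving treatment at week 12 is due at weeks 24, 36, 48 and 60.
- *Prednisone failures.* Under 4.1 and 6.7.1, a patient whose prednisone use counts as failure may remain on study treatment. That patient keeps the on-treatment schedule, including Cycle 7 Day 1, the primary-endpoint visit.

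**5. Size for organ-specific response.** Take the patients with a given organ involved at baseline. Let f be the share on secondary therapy at the assessment, q their response rate in that organ, and p the rate in the others.
- With the ORR conditions: (1 − f)p.
- Without them: (1 − f)p + fq.
- Difference: fq.

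The documents give no f or q. I assume f = 10% to 40% and q = 30% to 64%. The upper q borrows the pooled ORR for ECP in steroid-refractory disease (2.1.3) as an anchor only.
- Low end: 0.10 × 0.30 = 0.03, or 3 points; 46 × 0.03 = 1.4 patients.
- High end: 0.40 × 0.64 = 0.256, or 25.6 points; 46 × 0.256 = 11.8 patients.
- Middle case, f = 20%, q = 50%, p = 60%: 0.80 × 0.60 = 48% with the conditions, and 48% + 0.20 × 0.50 = 58% without.

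The patient counts suppose that all 46 have the organ involved; with fewer involved, the counts shrink in proportion.

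**6. DOR.** After a response on protocol treatment, a new chronic GVHD drug ends DOR, so adding that condition would change no end date. Two gaps remain. Relapse is neither an end event nor a stated censoring event, although 6.7.1 makes it a treatment failure. And nothing says that a responder must have responded before second-line therapy or relapse. No relapse rate is given, so I put no number on this part.

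**The case against.** The strongest reply is that the plan is silent rather than wrong. No sentence says that organ responses on rescue drugs count. The bullet on 24-week ORR by prednisone stratum also leaves out the conditions, although that ORR is defined with them in 1.1.2, so the short bullets may be list shorthand. Follow-up visits run from the end of treatment and have no window tying them to 24 weeks or 1 year. This stands to the extent that the text permits the counting and does not prescribe it. It does not remove the gap, because the prednisone failures who stay on treatment have no timing problem.

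On DOR, a reader might infer that time on second-line drugs is credited to the protocol treatment. The documents do not support that for a response reached on protocol treatment, since new therapy and death both end DOR. On steroids, DOR is stricter than the ORR: any new corticosteroid started for chronic GVHD ends it, while prednisone up to 0.25 mg/kg/d is not a primary-endpoint failure (4.1). It is also fair that DOR may be meant to describe GVHD control alone, with relapse reported separately as RR and within FFS. If that is the intent, the plan still has to say what happens to DOR at relapse.

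A reader might extend the point to the changes in NIH global and reported severity scores, and assign the worst category after death, relapse or secondary therapy. I do not propose this. It would give the worst GVHD severity to a patient whose malignancy relapsed while GVHD was controlled, and other strategies are as defensible.

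**Conclusion.** The point holds as a gap in the definitions of secondary endpoints. For organ-specific response all three ORR conditions are missing, and patients who have failed the ORR can be assessed and counted. For DOR only relapse of the underlying disease is missing, together with the requirement that the response come first.

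The size, about 3 to 26 points for an organ rate, rests wholly on assumed switching and response rates and shows scale only; it is not a forecast. A reader might infer that the trial's efficacy conclusion is at risk. It is not: the primary ORR, the 1-year ORR and FFS carry the conditions, the type I error and power are as stated, and neither affected endpoint has a decision threshold. The change is worth making because it is cheap and removes a post hoc choice in a trial without a control arm.

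**What to change.** 1. In 1.2.2 and 12.4.2, add to organ-specific response the qualifier that the 1-year ORR already has, "without secondary systemic immunosuppression and no recurrent malignancy or death". State that secondary immunosuppression is defined as for the primary endpoint, and that patients who do not meet the qualifier count as non-responders in each organ involved at baseline.
2. In 1.2.2, 12.4.2 and 12.4.3, add relapse of the underlying disease as an event that ends DOR, and require the qualifying response to precede any failure event.

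The cost is endpoint wording only. Secondary therapy, relapse and survival are already followed (Table 7, 9.5), so no new data are needed. Reported organ response rates would be somewhat lower and DOR somewhat shorter. Sample size and the primary test do not change.

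### Section 12.4.2 switches reversible status-at-visit endpoints to Kaplan-Meier once anything is censored, without defining censoring; the method then estimates the wrong quantity

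*Combined protocol and SAP*

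**What the plan says.** Section 12.4.2 (Efficacy) gives a two-part rule. The default is "Observed proportions and exact binomial confidence intervals will be reported for binary endpoints with no censored events". The list that follows begins "These may include withdrawal from immunosuppressants at 1-year, the overall response at 24 weeks stratified by current prednisone use" and goes on to 1-year overall response, organ response at 24 weeks and 1 year, absence of recurrent malignancy, absence of new systemic treatment for chronic GVHD, and a prednisone dose of at most 0.5 mg/kg/d at 24 weeks. The second part is "Kaplan-Meier methods will be used for these binary endpoints if there are censored events". No section says what a censored event is for any of these endpoints, or recasts them as times to an event.

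Three neighbouring rules matter:

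- **Primary endpoint** (Sections 12.1 and 12.4.1, Part 2): "Withdrawal or progression prior to 24 weeks or missing 24-week assessment will be considered non-response".
- **Non-relapse mortality and relapse** (Section 12.4.2): "NRM and RR will be treated as competing risks and analyzed by computing nonparametric subdistribution functions".
- **1-year overall response** (Sections 1.2.2 and 12.4.2): defined as response "without secondary systemic immunosuppression and no recurrent malignancy or death".

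The other two long-term status endpoints have no such clause. They read only "The proportion of patients who have withdrawn all immunosuppressants at 1-year" and "Organ-specific response rates at 24 weeks and 1-year as determined by the NIH Consensus Development Project Criteria".

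**The concern.** Kaplan-Meier estimates the distribution of the time to a first event. Most endpoints on this list are states that a patient is or is not in at a given visit, and the plan itself treats them as reversible. Duration of response ends at progression from best response, and Section 6.6.4 allows an immunosuppressant to be raised again if chronic GVHD worsens during its taper. A Kaplan-Meier estimate of first attainment counts such a patient as a success for good.

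The trigger is realistic. Section 6.7.2 takes patients off study at their own request, at the investigator's judgment or when lost to follow-up. Section 9.3 follows non-progressors for GVHD progression for 6 months after the end-of-treatment visit, while Section 9.5 gives 12 months after treatment for all patients. On the shorter reading, a patient who stops at month 3 has that visit at about month 4 and leaves GVHD follow-up at about month 10, before the 1-year landmark.

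Two things are at stake. The long-term rates may answer a different question from the 24-week rate they are meant to extend. And the choice of estimator would depend on the data, through a term that is left undefined.

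**Working it through.** **The plan's own figure.** The documents state no figure for these secondary endpoints. The only computed efficacy figure is for the primary design (40% against 60%; stop at 7 or fewer of 16; reject at 24 or more of 46). The sum over x = 8 to 16 of P(Bin(16, p) = x) × P(Bin(30, p) ≥ 24 − x) gives 0.0486 at p = 0.40 and 0.8006 at p = 0.60. Both match Section 12.4.1. That calculation uses counts, so the Kaplan-Meier sentence does not touch it.

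**Step 1: ever achieved against status at the visit.** Assume 46 patients, of whom 30 respond at some time and 6 of those lose response before the visit. Suppose no one is censored before responding.

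- Ever responded: 30/46 = 65.2%
- In response at the visit: (30 − 6)/46 = 24/46 = 52.2%

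The gap of 6/46 = 13.0 points does not depend on how deaths are coded.

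**Step 2: the stratified 24-week response.** This is the primary outcome split by prednisone use. A patient who withdraws, or misses the 24-week assessment, is a non-responder under Section 12.4.1. Section 12.4.2 would allow the same patient to be treated as censored in the stratified analysis. The strata then need not add up to the primary result.

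**Step 3: competing events, for immunosuppressant withdrawal and organ response only.** Let R be the true 1-year cumulative incidence of the favourable event and D that of death, relapse or secondary therapy. Both are assumptions, since the documents give no rates. With constant cause-specific hazards over the year:

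- total hazard H = −ln(1 − R − D)
- hazard of the favourable event h = H × R/(R + D)
- Kaplan-Meier estimate if competing events are censored = 1 − exp(−h)

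For R = 0.40 and D = 0.30: H = −ln(0.30) = 1.204; h = 1.204 × 0.40/0.70 = 0.688; estimate = 1 − exp(−0.688) = 0.497.

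| True R | D = 0.10 | D = 0.20 | D = 0.30 |
|---|---|---|---|
| 0.30 | 0.318 | 0.340 | 0.368 |
| 0.40 | 0.426 | 0.457 | 0.497 |
| 0.50 | 0.534 | 0.577 | 0.634 |
| 0.60 | 0.644 | 0.701 | 0.785 |

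The excess runs from about 2 to 19 points. It is zero if no competing event is censored.

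**Step 4: dependence on timing.** Take 46 patients with 18 favourable and 9 competing events. The proportion is 18/46 = 39.1%. If all 9 competing events come first and are censored, Kaplan-Meier gives 18/37 = 48.6%. If they all come last it gives 39.1%. In random order it averages 44.5%.

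**Step 5: an event-free endpoint for contrast.** For absence of recurrent malignancy, assume 10% relapse and 10% death. Kaplan-Meier with deaths censored gives 0.894 relapse-free, against 0.900 for one minus the cumulative incidence and 0.80 alive and relapse-free. The direction therefore depends on the comparator, and upward bias is not general.

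**The case against.** A reader might infer that the plan censors deaths, relapses and dropouts, and so inflates every long-term response rate. The documents do not support that.

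- Kaplan-Meier is the fallback. With nothing censored, the rule is the exact binomial proportion.
- No section says that death or relapse is censored. If these are scored as failures, they do not trigger the switch.
- For 1-year overall response the definition already makes death, recurrent malignancy and secondary systemic immunosuppression failures. Only withdrawal and loss to follow-up are open.
- The non-response rule is stated for the primary outcome and the competing-risk rule for non-relapse mortality and relapse. A different rule elsewhere is inconsistent practice, but it does not contradict either sentence.
- The list includes event-free endpoints, for which a time-to-event method under censoring is ordinary. Deleting the sentence outright would leave them without a rule.
- Non-informative loss to follow-up does not inflate Kaplan-Meier in this way, and under Section 9.5 stopping treatment is not dropout.
- These are descriptive secondary rates. At the low end the shift is small: an assumed true 25% with 15% competing events reads 27%, while the exact 95% interval for 12/46 is about 14% to 41%.

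All of this stands, and it limits the claim. It does not answer Steps 1 and 2. Once the switch is triggered, the stated method does not estimate status at the visit, however deaths are coded.

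**Conclusion.** The point holds in a limited form. For the status-at-visit endpoints, Section 12.4.2 prescribes an unsuitable method whenever something is censored, and leaves the trigger undefined. This is more than missing detail, because a specific method is named.

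The firm part is the mismatch between ever achieved and status at the visit, together with the possible failure of the stratified 24-week response to reconcile with the primary result. The 13-point gap is illustrative; its size depends on how many patients lose the state.

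The conditional part is inflation from censored competing events. It applies only to immunosuppressant withdrawal and organ response, where the plan is silent on death and relapse. It rests on assumed rates and constant hazards, and disappears if those events are not censored or all fall after the last favourable event. The primary endpoint, its missing-data rule and the Simon boundaries are unaffected. The sponsor should make the change, but no go/no-go decision turns on it.

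**What to change.** Narrow the Kaplan-Meier sentence rather than delete it.

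1. State that it does not apply to 1-year overall response, 24-week response by prednisone stratum, organ response at 24 weeks and 1 year, withdrawal of all immunosuppressants at 1 year, or the 24-week prednisone-dose endpoint.
2. Report each of these as a proportion with an exact interval, counting death, relapse, secondary therapy, withdrawal and missing assessment as not achieved, in line with the primary-endpoint rule.
3. Name one efficacy population for them and reconcile it with Section 12.2.3, which requires at least two weeks of combined therapy.
4. For the stratified response, say where a patient with no 24-week visit is placed, so that the strata add up to the primary result.
5. If time to immunosuppressant withdrawal is wanted, use cumulative incidence with death, relapse and secondary therapy as competing events.
6. Keep Kaplan-Meier for failure-free survival, overall survival and duration of response. For the event-free endpoints, define event and censoring and use time-to-event methods with competing risks where relevant; absence of recurrent malignancy should be consistent with the relapse-rate analysis.

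The cost is a few sentences of statistical text and no new data collection. Reported rates become slightly less favourable, and genuine loss to follow-up is counted conservatively.
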